6.0 DOSING DELAYS / DOSE MODIFICATIONS FOR SUBSEQUENT CYCLES

6.1 Suggested dose levels for dose adjustments

Table 4

Dose level	Cladribine (mg/m ² IV daily on days 1-5)*	Cytarabine (mg SQ twice daily on days 1-10)
1	5	20
-1	3.75	15
-2	2.5	10
-3	1.25	5

*3 days in consolidation

6.1.2. Dose levels different than dose described above may be allowed after discussion with the PI and documentation of the discussion.

6.1.3 Dose reductions for uproleselan are not planned. If there is a clinically significant grade 3 toxicity deemed related to uproleselan, it will be discontinued and patients will continue with chemotherapy alone.

Table 5

Non-Hematologic Toxicity	
Drug-related Grade 2 Toxicity	
Initiation of a treatment cycle will be delayed if a > Grade 1 non-hematologic toxicity has occurred or worsened and not yet returned to < Grade 2 prior to the start of the next cycle.	
Description of Event: Non-Hematologic	Dose Modifications
Non-hematologic Grade 3 adverse event	Hold therapy until recovery to Grade ≤1, then re-start and reduce one dose level. If toxicity recurs again, hold therapy until recovery to grade ≤1, then re-start and reduce one dose level. Dose reductions below dose level -3 will be considered on an individual basis after discussion with the principal investigator.
Drug-related grade 4 nausea, vomiting not optimally managed.	Study drug should be discontinued
Persistent grade 2 toxicity considered clinically significant or upon patient's request	Consider holding therapy until recovery to Grade ≤1, then re-start and reduce one dose level. If toxicity recurs again, hold therapy until recovery to grade ≤1, then re-start and reduce one dose level. Dose reductions below dose level -3 will be

	considered on an individual basis after discussion with the principal investigator.
Any occurrence of >/= drug related Grade 2 neurologic Events	The patient's study drug doses are to be re-evaluated in consultation with the Principal Investigator, and may be reduced according to the above parameters, or discontinued based on the event, and the time to resolution to ≤ Grade 1.

¹ Includes, but is not limited to, bacteremia, systemic fungal infections, cytomegalovirus (CMV) infection, *Pneumocystis carinii* pneumonia (PCP), disseminated *Varicella*, etc.

6.2 Patients in whom the toxicity occurs or persists beyond the planned completion of drug administration for the cycle will have the dose reductions implemented in subsequent cycles provided the toxicity has resolved as specified in the table above.

6.3 **Myelosuppression:** Patients with leukemias usually present with abnormal peripheral blood counts at the time therapy is started and myelosuppression is an expected event during the course of therapy for acute leukemias and myelodysplastic syndromes. Thus, no dose adjustments or treatment interruptions for myelosuppression will be planned for the first 4 weeks of therapy. After this time, treatment interruptions and dose adjustments may be considered according to the following guidelines:

6.3.1 Patients with neutropenia or thrombocytopenia as a consequence of the disease do not require treatment interruptions for myelosuppression. Dose-reductions in these patients should be considered in an individual case and discussed with the PI. The following guidelines can be used for these patients:

6.3.1.1 Patients with a response and pre-cycle counts of neutrophils $>1 \times 10^9/L$ and platelets $>50 \times 10^9/L$ who have sustained low counts of neutrophils $<0.5 \times 10^9/L$ or a platelet count $<20 \times 10^9/L$ for more than 2 consecutive weeks in the current cycle, may receive a subsequent course at 1 dose level reduction. A reduction of 2 dose levels may be considered if the myelosuppression was deemed severe and life threatening by the treating physician, and if it is in the patient's best interest.

6.3.1.2 If there are persistent peripheral blood blasts, or the bone marrow shows $>5\%$ blasts, continue treatment regardless of neutrophil and platelet count and give supportive care as needed.

6.3.1.3 If no marrow evidence of leukemia, hold therapy until recovery of granulocytes to $\geq 1 \times 10^9/L$ and platelets $\geq 60 \times 10^9/L$, then resume at same or 1 lower dose level according to guidelines mentioned above.

7.0 AGENT FORMULATION AND PROCUREMENT

Cladribine, and cytarabine are FDA approved and commercially available. Commercial supply will be used.

Uproleselan is an investigational agent and will be provided for the study by the manufacturer, GlycoMimetics. Expired or unused drug will be destroyed per institutional policy.

8.0 STATISTICAL CONSIDERATIONS

For Phase Ib, we will employ the Bayesian optimal interval (BOIN) design (Liu and Yuan, 2015; Yuan et al., 2016) to find the RP2D. The BOIN design is implemented in a simple way similar to the traditional 3+3 design, but is more flexible and possesses superior operating characteristics that are comparable to those of the more complex model-based designs, such as the continual reassessment method (CRM) (Zhou et al., 2018).

The target toxicity rate is $\phi = 0.3$ and the maximum sample size is 12 for phase Ib. We will enroll and treat patients in cohorts of size 3. DLTs are defined in section 4.1.3, and only those DLTs that occur within **cycle 1** will be used for dose finding. The BOIN design uses the following rule, optimized to minimize the probability of incorrect dose assignment, to guide dose escalation/de-escalation:

- if the observed DLT rate at the current dose is ≤ 0.236 , escalate the dose to the next higher dose level;
- if the observed DLT rate at the current dose is ≥ 0.359 , de-escalate the dose to the next lower dose level;
- otherwise, stay at the current dose.

For the purpose of overdose control, doses j and higher levels will be eliminated from further examination if $\Pr(p_j > 0.3 | \text{data}) > 0.95$ and at least 3 patients have been treated at dose level j , where p_j is the true DLT rate of dose level $j, j = 1, 2$. This posterior probability is evaluated based on the beta-binomial model $y_j | p_j \sim \text{binomial}(p_j)$ with $p_j \sim \text{uniform}(0,1)$, where y_j is the number of patients experienced DLT at dose level j . When the lowest dose is eliminated, stop the trial for safety.

The above dose escalation/de-escalation and elimination rule can be equivalently presented in Table 1, which will be used to conduct the trial. The steps to implement the BOIN design are described as follows:

1. Patients in the first cohort are treated at dose level -1.
2. To assign a dose to the next cohort of patients, conduct dose escalation/de-escalation according to the rule displayed in Table 1. When using Table 1, please note the following:
 - a. “Eliminate” means eliminate the current and higher doses from the trial to prevent treating any future patients at these doses because they are overly toxic.

- b. When we eliminate a dose, automatically de-escalate the dose to the next lower level. When the lowest dose is eliminated, stop the trial for safety. In this case, no dose should be selected as the RP2D.
- c. If none of the actions (i.e., escalation, de-escalation or elimination) is triggered, treat the new patients at the current dose.
- d. If the current dose is the lowest dose and the rule indicates dose de-escalation, treat the new patients at the lowest dose unless the number of DLTs reaches the elimination boundary, at which point terminate the trial for safety.
- e. If the current dose is the highest dose and the rule indicates dose escalation, treat the new patients at the highest dose.

3. Repeat step 2 until the maximum sample size of 12 is reached, or the trial is stopped early due to the elimination of the lowest dose.

Table 6. Dose escalation/de-escalation rule for the Boin design

Number of patients treated at current dose	3	6	9	12
Escalate if # of DLT <=	0	1	2	2
De-escalate if # of DLT >=		2	3	4
Eliminate if # of DLT >=		3	4	5

Note. # of DLT is the number of patients with at least 1 DLT. When none of the actions (i.e., escalate, de-escalate or eliminate) is triggered, stay at the current dose for treating the next cohort of 3 patients.

When phase Ib is completed, select the RP2D based on isotonic regression as specified in Liu and Yuan (2015). This computation is implemented by the shiny app “BOIN” available at <http://www.trialdesign.org>. Specifically, select as the RP2D the dose for which the isotonic estimate of the toxicity rate is closest to the target toxicity rate of 30%. In addition, in order for a dose to be declared as RP2D, at least 6 patients have been treated with at least 80% of the planned doses and the observed DLT rate at the RP2D level is < 30% (for example, <=1 out of 6, or <=2 out of 7~9, etc.).

Operation Characteristics

Table 2 shows the operating characteristics of the trial design based on 1000 simulations of the trial using shiny app “BOIN” available at <http://www.trialdesign.org>.

Table 7. Operating characteristics of the Boin design

	1	2	Number of Patients	% Early Stopping
Scenario 1				
True DLT Rate	0.3	0.48		
Selection %	58.9	27.4		13.7
% Pts Treated	70.2	29.8	11.2	
Scenario 2				

True DLT Rate	0.16	0.3		
Selection %	27.4	71.3		1.3
% Pts Treated	48.5	51.5	11.9	
Scenario 3				
True DLT Rate	0.4	0.55		
Selection %	56.4	12.6		31
% Pts Treated	82.3	17.7	10.4	

For phase II portion, a maximum of 25 patients will be enrolled and treated at the RP2D level. The Bayesian approach of Thall, Simon, Estey (1995, 1996) will be used to monitor overall response (OR) and treatment-related toxicities. The OR is defined as either CR or CRi and the assessment window for OR will be 2 cycles. The toxicities to be monitored include those defined in section 4.1.2 which during cycle 1.

Based on published data, an overall response rate (ORR) of 35% is expected for this population and we aim to improve the ORR by 25%, that is to say, the target response rate would be about 45%, while maintaining the toxicity rate at or below 30%. With a sample size of 25 patients, the 95% posterior credible interval for ORR will range between 0.27 and 0.63, assuming an ORR of 45% (i.e., 11 out of 25 patients having responses) and a non-informative prior of beta (1, 1).

Denoting the historical probabilities of ORR and toxicity rate by $\{p(\text{ORR}, H), p(\text{TOX}, H)\}$, the following monitoring rules will be applied:

- 1) Stop if $\text{Prob}\{p(\text{ORR}, H) + \delta_{\text{ORR}} > p(\text{ORR}, E) \mid \text{data}\} > 0.99$, where $\delta_{\text{ORR}} = 0.1$
- 2) Stop if $\text{Prob}\{p(\text{TOX}, H) < p(\text{TOX}, E) \mid \text{data}\} > 0.95$

where $p(\text{ORR}, E)$ and $p(\text{TOX}, E)$ are the true ORR and toxicity rates for the combination therapy. The priors of ORR and toxicities for the combination therapy are assumed to be Beta (1, 1) and Beta (0.6, 1.4), respectively. Patients will be monitored in cohort size of 5 according to the following stopping boundaries for ORR and toxicities.

Table 8: Stopping Boundaries for ORR and Toxicities, in cohort size of 5.

# Patients treated	Stop the trial if there are this many patients with CR/CRi:	Stop the trial if there are this many patients with toxicities:
5	never stop	4-5
10	0	6-10
15	0-2	8-15
20	0-3	10-20
25	Always stop with this many patients	Always stop with this many patients

The operating characteristics are summarized in the following table (based on simulations from 10,000 trials).

Table 9: Operating Characteristics for toxicity and futility monitoring.

P(TOX)	P(ORR)	P(Stop Early)
0.20	0.25	0.30
	0.35	0.09
	0.45	0.03
	0.55	0.02
0.30	0.25	0.36
	0.35	0.17
	0.45	0.11
	0.55	0.10
0.40	0.25	0.53
	0.35	0.39
	0.45	0.34
	0.55	0.34
0.50	0.25	0.76
	0.35	0.69
	0.45	0.67
	0.55	0.66

Multi Lean Desktop (version 2.1.0) was used to generate the toxicity and futility stopping boundaries and the operating characteristics table.

ANALYSIS PLAN

Summary statistics will be provided for continuous variables. Frequency tables will be used to summarize categorical variables. The overall response rate will be estimated along with the 95% credible interval. Similar analyses will be performed for other binary outcomes such as CR, CRi, etc. Overall survival (OS) is defined as the time interval between treatment start and the date of death or last follow-up, whichever occurred first. Remission duration (CRd) is defined, within patients who achieve CR/CRi, the time interval between the date of CR/CRi and the date of disease relapse, death or last follow-up, whichever occurred first.

Progression-free survival (PFS) is defined as the time interval between treatment start and the date of death, relapse or last follow-up, whichever occurred first. Kaplan-Meier method will be used to assess OS, CRd and PFS probabilities. Data from all subjects who receive any study drug will be included in the safety analyses. Subjects who entered the study and did not take any of the study drugs and had this confirmed will not be evaluated for safety. The severity of the toxicities will be graded according to the NCI CTCAE v5.0 whenever possible. We will follow standard reporting guidelines for adverse events. Safety data will be summarized by category, severity and frequency.

Cohort Summaries

The Investigator is responsible for completing toxicity summary reports and submitting them to the IND office Medical Affairs and Safety Group, for review and approval. These should be submitted as follows:

Phase 1B:

After the first 3 evaluable patients, complete cycle 1 of study treatment, and every 3 evaluable patients thereafter, prior to expanding/changing dose levels, or opening Phase II.

Phase II:

After the first 5 evaluable patients per cohort, complete cycle 2 of study treatment, and every 5 patients thereafter, until enrollment is complete.

A copy of the summary report should be placed in the Investigator's Regulatory Binder under "sponsor correspondence".

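### Phase Ib keeps enrolling to 12 patients even when no dose level, or not the level assigned, can still meet the plan's own RP2D conditions

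*Combined protocol and SAP*

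**What the plan says.** All of this is in section 8.0 (Statistical Considerations). The section fixes the size of this part of the study: "the maximum sample size is 12 for phase Ib". Accrual is by cohort: "We will enroll and treat patients in cohorts of size 3". The starting point is given in step 1: "Patients in the first cohort are treated at dose level -1". Two levels are studied, called here the lower (dose level -1) and the upper (dose level 1).

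Cohorts are assigned by the BOIN boundaries alone: "if the observed DLT rate at the current dose is ≤ 0.236 , escalate the dose to the next higher dose level"; de-escalate at 0.359 or above; eliminate a level when the posterior probability that its DLT rate exceeds 0.3 is above 0.95. Under step 2d, when de-escalation is indicated at the lowest level, the instruction is to "treat the new patients at the lowest dose unless the number of DLTs reaches the elimination boundary". Step 3 reads "Repeat step 2 until the maximum sample size of 12 is reached, or the trial is stopped early", and the only early stop it names is loss of the lower level under the elimination rule.

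Two further conditions then apply before a level may be declared RP2D. One is a minimum number treated: "at least 6 patients have been treated with at least 80% of the planned doses". The other is a ceiling on observed toxicity, namely that "the observed DLT rate at the RP2D level is < 30" per cent. They appear after Table 6, and none of steps 1 to 3 refers to them.

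**The concern.** The assignment rule and the declaration rule were written separately and can conflict once nine patients have been treated. BOIN tolerates a level at 4/9 DLTs because the evidence falls short of the elimination threshold. The declaration rule does not, since 4/9 cannot fall below 30% with only three more patients. BOIN also escalates for the last cohort, although an untried level cannot reach six patients with three places left.

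At stake are up to three of at most 12 phase Ib patients, treated at a level that phase Ib can no longer declare. The serious case is the one where no level can be declared: the dose-finding question is already answered in the negative, yet the plan requires another cohort.

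**Working it through.** **Inputs (section 8.0).** Cohorts of 3, at most four; start at the lower level; boundaries 0.236, 0.359 and 0.95 with a uniform prior. True DLT rates (lower/upper) from Table 7: 0.30/0.48, 0.16/0.30 and 0.40/0.55.

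**Boundaries.** For n = 3, 6, 9 the rule text gives escalate at ≤ 0, 1, 2; de-escalate at ≥ 2, 3, 4; eliminate at ≥ 3, 4, 5. In the available text of Table 6 the two lower rows seem shifted one column to the right, probably by text extraction, so the rule text was used.

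**Plan's own figures first.** Exact enumeration of all paths, with the isotonic pick and without the two extra RP2D conditions, against Table 7:

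| | Scenario 1 | Scenario 2 | Scenario 3 |
|---|---|---|---|
| Early stopping %, exact (stated) | 12.8 (13.7) | 1.4 (1.3) | 31.3 (31) |
| Mean patients, exact (stated) | 11.3 (11.2) | 11.9 (11.9) | 10.3 (10.4) |
| Selection %, exact | 62.1/25.2 | 28.3/70.4 | 58.3/10.4 |
| Selection %, stated | 58.9/27.4 | 27.4/71.3 | 56.4/12.6 |

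Three selection figures differ by 2.2 to 3.2 points, which is 1.6 to 2.3 standard errors of a 1000-run simulation. The other selection and early-stopping figures agree within 2 points, and mean patients within 0.1.

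**States after nine patients in which the assigned level cannot qualify.** Let b_k and u_k be the probabilities of k DLTs in a cohort of 3 at the lower and upper level.

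- (a) Lower level 4/9, upper untried. The posterior is Beta(5, 6) and Pr(p > 0.3) = 0.85, so there is no elimination and step 2d keeps the cohort there. Best result 4/12 = 33%. Probability 3·b1²·b2 + b2²·b0.
- (b) Lower level 2/9 = 22%. Cohort 4 opens the upper level, which ends with 3 patients. Probability b1²·b0 + b2·b0².
- (c) Lower 0/3, upper 2/3, then lower 0/6 or 1/6. The rule re-escalates. Best upper result 2/6 = 33%. Probability b0·u2·(b0 + b1).
- (d) Lower 0/3, upper 2/3 or 3/3, then lower 3/6. Best lower result 3/9 = 33%; the upper level is eliminated or at best 2/6. Probability b0·(u2 + u3)·b3.

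**Scenario 1.** b0 to b3 = 0.343, 0.441, 0.189, 0.027; u2 = 0.3594, u3 = 0.1106.

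- (a) 3 × 0.441² × 0.189 + 0.189² × 0.343 = 0.1103 + 0.0123 = 0.123
- (b) 0.441² × 0.343 + 0.189 × 0.343² = 0.0667 + 0.0222 = 0.089
- (c) 0.343 × 0.3594 × 0.784 = 0.097
- (d) 0.343 × 0.470 × 0.027 = 0.004

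| % of trials | Scenario 1 | Scenario 2 | Scenario 3 |
|---|---|---|---|
| (a) | 12.3 | 2.5 | 17.9 |
| (b) | 8.9 | 9.1 | 5.4 |
| (c) | 9.7 | 10.4 | 5.7 |
| (d) | 0.4 | 0.05 | 0.8 |
| Assigned level cannot qualify, (a) to (d) | 31.3 | 22.0 | 29.8 |
| No level can qualify, (a) + (d) | 12.7 | 2.5 | 18.7 |
| Other level already qualifies, (b) + (c) | 18.6 | 19.5 | 11.1 |

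**Effect of closing in (a) and (d) only.** Mean size falls by three times that share: 11.31 - 3 × 0.127 = 10.93; 11.92 - 3 × 0.025 = 11.84; 10.34 - 3 × 0.187 = 9.78. Expected DLTs fall by three times the share times the lower-level rate: 3.96 to 3.85, 2.75 to 2.74 and 4.41 to 4.18.

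**The case against.** **The last cohort is not useless.** It adds safety data and feeds the isotonic estimate. In states (b) and (c) the lower level already has at least 6 patients and a rate below 30%, so an RP2D remains available. This stands. A reader might infer that 22% to 31% of trials enrol a cohort with no prospect of any RP2D. The documents do not support that: those shares concern the assigned level only.

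**Continuing at 4/9 is deliberate.** Step 2d says so expressly, and 0.85 is below the plan's 0.95. That is true of the overdose rule. But the later 30% condition has by then ruled out the only level tried, so continuing cannot serve the purpose of finding an RP2D.

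**There is already a checkpoint.** The Cohort Summaries paragraph requires a toxicity report for review and approval after every 3 evaluable patients. It is a real safeguard, but it contains no test of whether a level can still qualify.

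**Redirecting the cohort to the qualifying level looks like the better remedy.** A reader might infer that it raises the chance of an RP2D. Closing when nothing can qualify and redirecting otherwise does raise it from 55.6% to 68.3% in Scenario 2, but only if the isotonic pick must itself pass with no fallback. On that reading Scenario 3 hardly moves (22.9% to 23.0%). If the pick is limited to eligible levels, the chance falls: 50.6% to 47.4%, 77.7% to 76.8% and 28.4% to 25.1%. In state (b), two or more DLTs among three added patients turn 2/9 into at least 4/12, with probability 22%, 7% and 35% in Scenarios 1 to 3. Redirection can therefore undo a level that already qualifies.

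**Table 6 read literally gives smaller figures.** With the rows as they stand in the text, the assigned-level shares are 16.0%, 13.4% and 10.7%, and the state with no declarable level does not arise. But early stopping would then be 33.5%, 6.9% and 58.0%, which does not match Table 7.

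**Conclusion.** The conflict is real and follows from the plan's own rules. The part that clearly needs repair is the 12.7%, 2.5% and 18.7% of trials (Scenarios 1 to 3) in which a fourth cohort is required although no level can be declared. In a further 18.6%, 19.5% and 11.1% the cohort goes to a level that cannot be declared while the other already meets both numeric conditions. There the plan owes a reason, but no RP2D is lost by its conduct if the pick may fall on the eligible level.

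The gain is modest: three fewer patients in the affected trials, and a fall in expected DLTs that comes from treating fewer patients. A claim that the present rule materially lowers the chance of an RP2D would depend on how the final pick is read, which is a separate question.

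The figures rest on the boundaries in the rule text, full cohorts of three, the start at the lower level and the Table 7 scenarios. The requirement that patients receive 80% of planned doses is not modelled; it could only make an assigned level harder to declare.

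**What to change.** Reconcile steps 2 and 3 with the RP2D conditions by adding a feasibility check before each cohort. For each level not eliminated, ask whether it could still reach at least 6 patients and an observed DLT rate below 30% if all remaining places, up to 12, were used there without a DLT.

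- If no level could, do not open the cohort, and close phase Ib with no RP2D. This leaves the chance of declaring an RP2D unchanged under either reading of the pick.
- If only the assigned level could not, the study team should state in advance whether phase Ib may close on the level that already qualifies, or why the cohort is still wanted. With closure, and the pick limited to eligible levels, the chance of an RP2D stays at 50.6%, 77.7% and 28.4%. Mean size, with closure in both situations, would be 10.37, 11.26 and 9.45.
- Do not write in an automatic redirection of patients to another level.

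Re-run Table 7 with the check and with the two RP2D conditions applied, since its current figures match selection without them. The cost is a short addition to step 2, one simulation re-run, and up to three fewer safety observations in the affected trials.

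### Table 7's selection percentages leave out the protocol's own conditions for declaring an RP2D, so they overstate how often phase Ib yields one

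*Combined protocol and SAP*

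**What the plan says.** Section 8.0 (Statistical Considerations) sets out phase Ib as a two-dose BOIN design: "We will enroll and treat patients in cohorts of size 3", and "the maximum sample size is 12 for phase Ib". At the end of phase Ib the instruction is to "select as the RP2D the dose for which the isotonic estimate of the toxicity rate is closest to the target toxicity rate of 30" per cent. The next sentence adds two conditions for declaring that dose. The first concerns exposure: "at least 6 patients have been treated with at least 80% of the planned doses". The second concerns toxicity, and asks that "the observed DLT rate at the RP2D level is < 30" per cent. The examples given there are at most 1 DLT in 6 patients and at most 2 in 7 to 9.

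The simulation results follow immediately: "Table 2 shows the operating characteristics of the trial design based on 1000 simulations of the trial using shiny app" (the table meant is numbered 7). Table 7 gives a selection percentage for each dose and an early-stopping percentage.

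The only outcome without a dose that the section spells out is elimination of the lowest dose: "When the lowest dose is eliminated, stop the trial for safety. In this case, no dose should be selected as the RP2D". For phase II, "a maximum of 25 patients will be enrolled and treated at the RP2D level".

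**The concern.** The two steps of the rule pull against each other. The first favours a dose whose estimate is near 30%; the second bars any dose observed at or above 30%. A final count of 2/6, 3/9 or 4/12 (33.3% each) can be the isotonic pick, but it cannot be declared. A design with this second step must sometimes finish phase Ib with a pick that fails, yet Table 7 has no place for such a trial.

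The RP2D is part of the primary objective (Section 1.0), and phase II enrols only at the RP2D. A reader of Table 7 would conclude that phase Ib yields an RP2D unless it stops for toxicity. The text also does not say whether a failed pick passes the choice to the other dose or means no RP2D. If that question is settled only after the DLT counts are known, the answer to the primary objective depends on a choice made with the data in view.

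**Working it through.** **Inputs from Section 8.0.** Two doses, starting at the lower; cohorts of 3; maximum 12 patients; escalate at an observed rate ≤ 0.236; de-escalate at ≥ 0.359; eliminate if Pr(p > 0.3 | data) > 0.95 under a uniform prior with at least 3 patients; stop if the lowest dose is eliminated. Table 7 columns 1 and 2 are taken as the lower and higher dose.

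**Boundaries.** The Table 6 columns are shifted in the extracted text, so the counts were derived from the written rule. At n = 3/6/9/12: escalate at ≤ 0/1/2/2, de-escalate at ≥ 2/3/4/5, eliminate at ≥ 3/4/5/7.

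**Assumed estimator.** The documents cite a source for the isotonic step but give no formula. I used (y + 0.05)/(n + 0.1), pooled with inverse-variance weights when the two doses are out of order, with eliminated doses excluded.

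**Step 1: row sums in Table 7.**
- Scenario 1: 58.9 + 27.4 + 13.7 = 100.0
- Scenario 2: 27.4 + 71.3 + 1.3 = 100.0
- Scenario 3: 56.4 + 12.6 + 31 = 100.0

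Every simulated trial that did not stop early is counted as naming a dose.

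**Step 2: reproduce Table 7.** Exact enumeration of all cohort paths, using the isotonic pick and nothing else (lower dose / higher dose / early stop, %):

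| Scenario (true DLT rates) | Table 7 | Isotonic pick alone |
|---|---|---|
| 1 (0.30 / 0.48) | 58.9 / 27.4 / 13.7 | 62.1 / 25.2 / 12.8 |
| 2 (0.16 / 0.30) | 27.4 / 71.3 / 1.3 | 28.3 / 70.4 / 1.4 |
| 3 (0.40 / 0.55) | 56.4 / 12.6 / 31 | 58.3 / 10.4 / 31.3 |

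The Monte Carlo standard error for 1000 runs is √(p(1−p)/1000), for example √(0.621 × 0.379/1000) = 1.5 points. The largest standardised gaps are about −2.1 (Scenario 1, lower dose) and +2.3 (Scenario 3, higher dose). About 8% of replicate 1000-trial tables deviate at least as much as the printed one. The early-stopping column is correct.

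**Step 3: apply the declaration conditions.** On the same paths, the pick is kept only if n ≥ 6 and y/n < 0.30, that is ≤ 1/6, ≤ 2/9 or ≤ 3/12. Results are lower / higher / no RP2D, %:

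| Scenario | Failed pick means no RP2D | Other dose used if it qualifies |
|---|---|---|
| 1 | 32.4 / 5.5 / 62.0 | 45.0 / 5.5 / 49.4 |
| 2 | 21.1 / 34.5 / 44.4 | 43.2 / 34.5 / 22.3 |
| 3 | 21.2 / 1.6 / 77.1 | 26.8 / 1.6 / 71.6 |

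Rows may miss 100 by 0.1 through rounding. The chance of declaring any RP2D, as 100 minus the no-RP2D figure, against Table 7 (100 minus early stopping):
- Scenario 1: 38.0–50.6%, Table 7 86.3%
- Scenario 2: 55.6–77.7%, Table 7 98.7%
- Scenario 3: 22.9–28.4%, Table 7 69.0%

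**Step 4: where the loss arises.** With no fallback, the no-RP2D trials split into early stop / pick with fewer than 6 patients / pick with at least 6 patients but a rate of 30% or more:
- Scenario 1: 12.8 / 5.5 / 43.8%
- Scenario 2: 1.4 / 7.5 / 35.5%
- Scenario 3: 31.3 / 2.8 / 43.0%

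The below-30% condition does most of the work. The pick ends at exactly 2/6, 3/9 or 4/12 in 24.8%, 24.3% and 19.4% of trials.

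**Step 5: one path by hand (Scenario 2).** Suppose 0/3 at the lower dose, then 3/9 at the higher without de-escalating.
- Lower dose: 0.84³ = 0.5927.
- Higher dose, cohort probabilities for 0, 1, 2, 3 DLTs at 0.30: 0.343, 0.441, 0.189, 0.027. The admissible sequences are (0,0,3), (0,1,2), (0,2,1), (1,0,2) and (1,1,1): 0.0032 + 3 × 0.0286 + 0.0858 = 0.1747.
- Product: 0.5927 × 0.1747 = 0.104.

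In these 10.4% of trials the pick is the higher dose. It fails at 33.3%, and the lower dose has only 3 patients, so neither can be declared under either reading.

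**Step 6: size of the gap in the rule.** The pick fails while the other dose qualifies in 12.6%, 22.1% and 5.5% of trials (62.0 − 49.4, 44.4 − 22.3, 77.1 − 71.6).

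**The case against.** The best defence separates selecting from declaring. Table 7 is captioned as the BOIN design, labels its rows as selection, and comes from the BOIN app, so its figures are right for the isotonic step. The conditions that follow are a sequential filter, and a pick that fails it simply yields no RP2D. That reading of the filter is reasonable, and it is the no-fallback column above. It does not rescue the table: the isotonic sentence itself speaks of selecting the RP2D, the table is introduced as describing the trial design, and nothing says the conditions were left out. Even on this reading, the chance of no RP2D is far above the figure shown.

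Four qualifications stand.

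- The overstatement is not in every cell. If the other dose may be used, the lower dose in Scenario 2 is declared more often than printed (43.2% against 27.4%).
- In Scenario 3 both doses exceed the target, so fewer declarations are protective.
- The example of 2 in 7 to 9 includes denominators that full cohorts of 3 cannot give. The observed rate may therefore be meant over a subset of patients, whereas the calculation uses all treated patients.
- Table 7 triggers no action in the trial, and Section 8.0 (Cohort Summaries) requires toxicity reports to be reviewed and approved before phase II opens. The harm is to planning and to pre-specification, not a route to a more toxic dose.

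**Conclusion.** The concern holds. Table 7 gives the operating characteristics of the isotonic pick, not of the RP2D rule as written. The true chance of ending phase Ib without an RP2D is 49.4–62.0%, 22.3–44.4% and 71.6–77.1% in Scenarios 1 to 3, where the table shows 13.7%, 1.3% and 31%. In Scenario 2 the at-target higher dose is declared in 34.5% of trials under either reading, against 71.3% printed; simulation error cannot explain a gap of about 37 points. The rule is also incomplete, because it does not state what follows when the pick fails.

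These figures assume the estimator described above, all treated patients as the DLT denominator, and no loss to the 80%-of-planned-doses requirement. With that denominator, the 80% requirement could only reduce declarations further. The effect shrinks if toxicity is low: under assumed true rates that are not in the documents, no RP2D is declared in 2.9–8.5% of trials at 0.05/0.10 and 11.9–28.1% at 0.10/0.20. This must be fixed because it concerns the primary objective and the missing rule has to be settled before data are seen.

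**What to change.** - Re-simulate Table 7 with the full RP2D rule and replace the selection percentages. Keep the early-stopping column and add a separate column for trials in which no RP2D is declared.
- Add a sentence, before data are seen, saying whether the other dose is considered or no RP2D is declared when the isotonic pick fails a condition.
- Reconcile the closest-to-30% selection step with the below-30% condition, and state which patients form the denominator of the observed DLT rate.

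This point asks for no change to the escalation or elimination boundaries or to the sample size. The cost is one simulation run, one revised table and a few lines of text. The drawback is that the stated dose-selection performance becomes less favourable in Scenarios 1 and 2.
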